## Clinical Protocol

### FIH-3

Doc No: CLINP1837  
Revision: D  
DCO No: 25-009  
Effective Date: 02/06/25

Amplifi System-related complication and the loss or damage to sites for dialysis access or the need to convert an AV fistula to an AV graft or hemodialysis catheter; not inclusive of the placement of pressure dressings, the placement or removal of skin sutures, the creation of an AVF or AVG, or the placement or removal of a hemodialysis catheter.

- *Amplifi System-related complication* is defined as any untoward medical occurrence, unintended disease or injury, or untoward clinical sign or abnormal lab finding related to the placement, use, operation, or removal of the Amplifi System; not inclusive of mild-moderate hand, wrist, arm, neck, or face swelling that resolves within 7 days after the end of the Amplifi System treatment period.
- *Amplifi System treatment period* is defined as starting when a needle is used to access the internal jugular vein or cephalic vein at the start of Amplifi System placement and ending when the Inflow Catheter and Distal Outflow Catheter have been completely removed and any related incisions have been closed.
- *Aneurysm of Study AVF* is defined as expansion of the intimal, medial, and adventitial layers of the wall of a segment of outflow vein of a Study AVF in the region between the Study AVF anastomosis and the axilla that requires treatment through an interventional procedure or surgery.
- *Anti-platelet agent* is defined as a pharmaceutical that is approved for use to decrease platelet aggregation and inhibit thrombus formation.
- *AVF circuit* is defined as the region starting with the origin of the inflow artery and continuing to the junction of the superior or inferior vena cava and the right atrium.
- *AVF creation* is defined as the making of an opening between the lumen an artery and vein for the purpose of creating a vascular access for hemodialysis, inclusive of interventional and surgical methods.
- *AVF-related intervention* is defined as an interventional procedure or surgery after the creation of an AVF to evaluate an AVF, promote maturation of an AVF, achieve or maintain patency of an AVF, or reduce AVF blood flow, including thrombectomy, pharmacologic thrombolysis, angioplasty and stenting of an inflow artery, outflow vein, or ipsilateral central vein, embolization or surgical ligation of an AVF tributary vein, surgical revision of an AVF anastomosis, the cutting, removal or otherwise rendering of a valve in an AVF outflow vein incompetent, resection of a segment of outflow vein, unplanned superficialization of a segment of outflow vein, and surgical or interventional treatment of ipsilateral arterial steal.
- *AVF maturation* is defined as an AVF having a mid or distal forearm outflow vein diameter  $\geq 6$  mm and blood flow  $\geq 500$  mL/min, both as measured by ultrasound, with AVF blood flow imputed from distal brachial artery blood flow.
- *AVF thrombosis* is defined as the formation of thrombus in a component of the AVF circuit, inclusive of occlusive and non-occlusive thrombus.
- *Bleeding diathesis* is defined as an unusual susceptibility to bleeding, including due to hypocoagulability.
- *Central venous and right atrial thrombus* is defined as intraluminal thrombus in the axillary, subclavian, brachiocephalic, femoral, external iliac, internal iliac, common iliac, or internal jugular veins, the superior or inferior vena cava or the right atrium, inclusive of occlusive and non-occlusive thrombus.

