## Clinical Protocol FIH-3

Doc No: CLINP1837  
Revision: D  
DCO No: 25-009  
Effective Date: 02/06/25

embolism, major thrombosis, major thromboembolism, major hemolysis, or major thrombocytopenia; local infection

- Amplifi System-related re-hospitalization or prolonged hospitalization;
- Amplifi System-related major surgery or major interventional procedure; or
- any Amplifi System-related complication determined to be an Amplifi System-related major complication by both an Investigator and the Medical Monitor.

\*Detailed definition of Major Device-Related Adverse Events is described in **Attachment 1: Definitions**

- **Rate of Occurrence of Cannulation-related Complications** [Timeframe: from AVF creation through end of follow-up period]

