- *Amplifi System-related re-hospitalization* is defined as an admission to a hospital due to an Amplifi System-related complication, not inclusive of a visit to an emergency room, clinic, or outpatient facility that does not result in admission to a hospital.
- *Amplifi System-related prolonged hospitalization* is defined as a prolongation of a hospital admission due to an Amplifi System-related complication.
- *Amplifi System-related major surgery* is defined as an open surgery involving an incision and the cutting of the body to address a life-threatening adverse event, to prevent disability, or to treat or prevent permanent impairment or damage to a vital body structure or function due to an Amplifi System-related complication; not inclusive of the placement of pressure dressings, the placement or removal of skin sutures, the creation of an AVF or AVG, or the placement or removal of a hemodialysis catheter.
- *Amplifi System-related major interventional procedure* is defined as an interventional procedure to address a life-threatening adverse event, to prevent disability, or to treat or prevent permanent impairment or damage to a vital body structure or function due to an

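### The definition of a major interventional procedure names conversion of the AVF as part of the event and then excludes the procedures that achieve it, so this safety component does not reliably capture device-caused conversions

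*Protocol*

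**What the plan says.** Section 4.5 of the protocol lists the Major Device-Related Adverse Event rate first among the safety measures, counted from implantation to 30 days after device removal and AVF creation. One component is "Amplifi System-related major surgery or major interventional procedure; or" and the reader is sent to the definitions appendix for detail.

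In Appendix 1 this interventional component opens with a seriousness test: "is defined as an interventional procedure to address a life-threatening adverse event, to prevent disability, or to treat or prevent permanent impairment". Lasting harm to vital structures or functions is covered too. The cause must be a device-related complication, and here the text adds a clause: "Amplifi System-related complication and the loss or damage to sites for dialysis access or the need to convert an AV fistula to an AV graft". The same sentence then passes straight from conversion into its exclusions: "or the need to convert an AV fistula to an AV graft or hemodialysis catheter; not inclusive of the placement of pressure dressings". Last on that list come "the creation of an AVF or AVG, or the placement or removal of a hemodialysis catheter".

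The definition of major surgery, just before it, applies the same seriousness test to open surgery and ends with the same access-procedure exclusion. It has no clause on loss of access sites or conversion.

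The composite also counts, among others, major thrombosis, "Amplifi System-related re-hospitalization or prolonged hospitalization" and "any Amplifi System-related complication determined to be an Amplifi System-related major complication by both an Investigator and the Medical Monitor".

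**The concern.** There are two faults in one sentence.

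- **Conversion is both in and out.** Converting an AVF to a graft or catheter means creating a graft or placing a catheter. The definition names the first and excludes the second, with no qualifier such as planned or routine.
- **The role of access loss is unclear.** Joined by 'and', it can be read as a condition that must hold in addition to the seriousness test. An interventional procedure for a life-threatening device complication that spares the access would then not qualify, whereas open surgery for the same complication would.

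The event is foreseeable. Section 12.2.6 lists vascular injury, vascular thrombosis and AVF thrombosis as potential events. Section 7.4 provides for another vascular access when an AVF is judged not to be in the Subject's interest after treatment. If device damage is the reason, the procedure that supplies the new access falls under the exclusion.

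Section 4.1 says the safety analysis should confirm that major complications lie in an acceptable range. Two assessors reading this sentence could classify the same Subject differently, and in so small a study that changes the reported rate visibly.

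**Working it through.** The protocol states no figure for this rate, so there is nothing to reproduce. The check is to put plausible events through the text and then to size one misclassification.

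**Step 1: events against the two procedure definitions (Appendix 1).** Each event is assumed to be caused by an Amplifi System-related complication and, where a procedure is done, to meet the seriousness test.

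1. *The access is converted by creating a graft.* Need to convert: named. Graft creation: excluded. If done by open surgery, the major surgery definition excludes it as well. Result: contradictory under one definition, not counted under the other.
2. *The access is converted by placing a new hemodialysis catheter.* Named and excluded in the same way. Result: contradictory.
3. *An access site is damaged and treated by another intervention, such as angioplasty.* Loss or damage is a separate limb and the exclusion does not touch angioplasty. Result: counted on either reading of 'and'.
4. *An intervention treats a life-threatening complication and no access is lost.* Counted if 'and' only extends the list of reasons for the procedure; not counted if it adds a condition. Result: depends on the reader.
5. *The AVF is lost and dialysis continues through the catheter already in place.* All Subjects enter with a tunneled catheter (Section 4.6), so this can happen without any procedure. Result: not counted, because no interventional procedure took place; the exclusion is not the reason.

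**Step 2: other routes into the composite (Section 4.5 and Appendix 1).**

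- Hospitalization: needs an admission or a prolonged stay due to a device-related complication.
- Major thrombosis: needs imaging and a thrombectomy, thrombolysis or long-term anticoagulation, and leaves out a thrombectomy done during AVF creation. Section 7.5 foresees thrombus being removed at that point after a pump stoppage.
- Catch-all: needs two assessors to agree that the complication is major. The underlying term is broad ("any untoward medical occurrence, unintended disease or injury, or untoward clinical sign or abnormal lab finding related to the placement, use, operation, or removal"), with only transient mild-to-moderate swelling left out. The second assessor is the Medical Monitor in Section 4.5 but the CEC in Appendix 1.

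**Step 3: size of one missed Subject.** Input: n of at most 10 (Section 14.1).

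- Shift in the rate: 1/n, which is at least 1/10 = 10 percentage points.
- Exact (Clopper-Pearson) 95% interval for 0/10: lower limit 0; upper limit 1 − 0.025^(1/10) = 0.308.
- For 1/10: lower limit 1 − 0.975^(1/10) = 0.0025; upper limit solves (1 − p)^10 + 10p(1 − p)^9 = 0.025, giving p = 0.445.

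If the missed event is the only one among 10 Subjects, 10% (0.3% to 44.5%) is reported as 0% (0% to 30.8%).

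**The case against.** The exclusion has an evident purpose. Subjects arrive with a tunneled catheter and are scheduled for AVF creation, so the planned access procedures must not score as major events. On a sympathetic reading, need to convert is a qualifying circumstance, the exclusion covers only routine access work, and 'and' merely extends the reasons for the procedure. That reading is possible, but nothing in the wording selects it. A component that can be read either way is not well fixed.

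A reader might infer more: that device-caused loss of the access cannot enter the safety outcome at all, or that this component is practically empty. The documents support neither. The limb on loss of or damage to access sites survives whenever another interventional procedure is used. Hospitalization, major thrombosis and the catch-all remain open. Outside the composite, Section 14.2.3 reports all adverse events by type, with severity and relatedness, and Table 3 has access-related thrombosis, procedures and surgeries documented for all access types at follow-up. The harm would be visible in the study report even if the composite missed it.

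The size is also conditional. The protocol gives no frequency for such an event, and Section 3.2.3 reports no serious adverse events or re-hospitalizations in the 10 earlier subjects. The study is descriptive, is not powered, and sets no numerical limit for this rate. These points limit the consequence; they do not remove the contradiction.

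**Conclusion.** The definition contradicts itself on conversion to a graft or catheter, and it leaves open whether access loss is an alternative or an added condition. Device-caused conversions, and interventions for serious device complications without access loss, are therefore not reliably captured by this component and may reach the composite only by other routes, of which the broadest is discretionary. The finding concerns unreliable capture by one component; the harm is not shut out of the safety outcome.

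The shift of at least 10 percentage points rests on three assumptions: such an event occurs within the safety window, no other component catches it, and the two assessors do not call it major. How likely that is cannot be derived from the protocol. The wording should be corrected, because an event that a definition names should not depend on other components to be counted.

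**What to change.** Reword Appendix 1 in two places.

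1. In the major interventional procedure definition, make loss of or damage to access sites, or need to convert the AVF, an alternative qualifying criterion ('or that results in') instead of a clause joined by 'and'.
2. In both the major interventional procedure and the major surgery definitions, limit the AVF, graft and catheter exclusion to access procedures that are not conversions caused by an Amplifi System-related complication. Copying the structure of the major surgery definition is not enough: it carries the same exclusion and has no access-loss limb.

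It would also help to state whether a return to dialysis through the existing catheter, with no new procedure, is meant to count, and to name the same second assessor for the catch-all in Section 4.5 and Appendix 1.

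The cost is a few lines of outcome wording, with no change to treatment or schedule. The reported event rate may come out slightly less favourable.

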## Clinical Protocol FIH-3

Doc No: CLINP1837  
Revision: D  
DCO No: 25-009  
Effective Date: 02/06/25

- *Central venous angioplasty* is defined as an interventional procedure or surgery to enlarge the lumen of the axillary, subclavian, or brachiocephalic veins, or the superior vena cava.
- *Central venous occlusion* is defined as the complete blockage of the axillary, subclavian, or brachiocephalic veins, or the superior vena cava.
- *Central venous stenosis  $\geq 50\%$*  is defined as a  $\geq 50\%$  narrowing of the lumen of an axillary, subclavian, or brachiocephalic vein, or the superior vena cava, wherein a normal segment of vein adjacent to the narrowed segment is used as a reference vessel for making the determination and the maximum observed diameter reduction is used, inclusive of measurements made with ultrasound imaging, venography, or MRI.
- *Central venous stent placement* is defined as an interventional procedure or surgery wherein a metal tube is permanently placed in the lumen of the axillary, subclavian, or brachiocephalic veins, or the superior vena cava for the purpose of keeping the vessel open.
- *Coagulopathy* is defined as a derangement of hemostasis resulting in either excessive bleeding or clotting.
- *Gastrointestinal bleeding* is defined any form of hemorrhage or bleeding that occurs in the gastrointestinal tract from the mouth to the anus.
- *Hemodialysis catheter placement* is defined as the placement of a new hemodialysis catheter, including the replacement of an existing hemodialysis catheter with a new catheter, and not inclusive of the repositioning of a catheter where the same catheter remains in the Subject before and after the procedure.
- *Hemodialysis catheter-related bloodstream infection* is defined as the growth of the same organism from a hemodialysis catheter and a peripheral venipuncture (or a suitable surrogate such as a hemodialysis blood line) in a patient with clinical signs of a bloodstream infection and no alternative source of bloodstream infection other than the hemodialysis catheter.
- *Indicated for forearm radiocephalic AVF creation based on an Investigator's standard practice* is defined as:
  - indicated for wrist or distal forearm radiocephalic AVF creation based on an Investigator's standard practice;
  - a wrist or distal forearm cephalic vein diameter of  $\geq 1.75$  mm and  $\leq 3.2$  mm at the proposed AVF creation site;
  - a forearm cephalic vein demonstrating patency and continuity of blood flow from the proposed AVF creation site to and through the upper arm through at least one of:
    - the upper arm cephalic vein;
    - the median cubital vein to the upper arm cephalic or basilic vein; or
    - the perforator vein to the deep venous system

with no occlusion or stenosis  $\geq 50\%$  along the course of the proposed AVF outflow from the proposed AVF creation site to and through the upper arm to the axilla, as determined by duplex ultrasonography; **and**

- a wrist or distal forearm radial artery diameter of  $\geq 2.0$  mm at the proposed AVF

## Clinical Protocol

### FIH-3

Doc No: CLINP1837  
Revision: D  
DCO No: 25-009  
Effective Date: 02/06/25

creation site.

- *Internal jugular vein suitable for Amplifi Inflow Catheter insertion* is defined as a widely patent internal jugular vein without thrombus and with a lumen diameter  $\geq 8.5$  mm (during Valsalva) that does not contain any catheter or intravascular implant and is deemed to be suitable for Inflow Catheter insertion by the Investigator.
- *Intervention-free AVF maturation* is defined as AVF maturation (as defined above) in the absence of any interventional procedure, surgery, or medical treatment to promote maturation of the AVF.
- *Interventional procedure, surgery, or medical treatment to promote maturation of the AVF of Study AVF* is defined as an interventional procedure, surgery, or a medical treatment intended to:
  - increase the diameter of a segment of an artery or vein in Study AVF circuit or increase Study AVF blood flow, including by angioplasty or stent placement, cutting, removing, or otherwise rendering a venous valve incompetent, resecting of a segment of outflow vein, and surgical revision of the Study AVF anastomosis;
  - remove thrombus from the lumen of the artery or vein in Study AVF circuit; and
  - reduce the flow of blood in Study AVF tributaries including by embolization or surgical ligation;and excluding planned superficialization of a segment of Study AVF outflow vein for the purpose of enabling easier cannulation.
- *Interventional procedure, surgery, or medical treatment to achieve or maintain functional patency of Study AVF* is defined as an interventional procedure, surgery, or a medical treatment intended to:
  - increase the diameter of a segment of artery or vein in Study AVF circuit or increase Study AVF blood flow, including by angioplasty or stent placement;
  - cut, remove, or otherwise render a venous valve incompetent;
  - surgically revise the Study AVF anastomosis;
  - remove thrombus from the lumen of the artery or vein in Study AVF circuit;
  - resect a segment of Study AVF outflow vein; and
  - reduce the flow of blood in Study AVF tributaries including by embolization or surgical ligation;inclusive of interventional procedures, surgeries, and medical treatments intended to promote maturation of Study AVF; and  
exclusive of planned superficialization of a segment of Study AVF outflow vein for the purpose of enabling easier cannulation.
- *Intracranial bleeding* is defined as any bleeding within the intracranial vault, including bleeding in the brain parenchyma and meningeal spaces.
- *Pseudoaneurysm of Study AVF* is defined as a locally contained hematoma of a Study AVF outflow vein with persistent blood flow in the hematoma and a neck between the hematoma and the Study AVF outflow vein that does not close spontaneously that is located between the Study AVF anastomosis and the axilla that requires treatment with an interventional

## Clinical Protocol

### FIH-3

Doc No: CLINP1837  
Revision: D  
DCO No: 25-009  
Effective Date: 02/06/25

procedure or surgery, inclusive of percutaneous injection of an agent intended to induce thrombosis.

- *Site Personnel* is defined as persons employed by the Site, other than Investigators, that are involved in the storage, placement, use, operation, maintenance, care, cleaning, monitoring, interaction with, removal, and disposal of the Amplifi System and its components.
- *Thrombophilia* is defined as a clinical tendency to thrombosis or molecular abnormalities of hemostasis that predispose to thrombosis.
- Treatment Failure is defined as “a subject will be classified as a treatment failure if they do not achieve the minimum required Amplifi treatment duration of 48 hours. This classification applies regardless of whether the subject has an arteriovenous fistula (AVF) created or not.”
  - **Device technical success** is defined as successful operation of the Amplifi system throughout the treatment period (from device implantation through device removal and AVF creation) without unplanned pump stoppages or device malfunctions that require intervention or prevent completion of the intended 48-hour treatment duration.
  - **Treatment success** is achieved when the Amplifi system operates without unplanned pump stoppages or device malfunctions, allowing for the full 48-hour treatment duration, and results in successful creation of an arteriovenous fistula (AVF) or meets the predefined clinical objectives as specified in the study protocol.
- *Vascular access for hemodialysis* is defined as an AVF, AVG, or hemodialysis catheter.
- *Vascular access-related hospitalization* is defined as admission to a hospital for treatment of a vascular access or a vascular access-related complication, not inclusive of a visit to an emergency room, clinic, or outpatient facility that does not result in admission to a hospital.
- *Vascular access steal syndrome* is defined as one or more signs or symptoms of ipsilateral hand ischemia that requires treatment with an interventional procedure or a surgery.
- *Wrist or distal forearm radiocephalic AVF* is defined as an AVF made with the radial artery and the cephalic vein, wherein the anastomosis is made in the hand, wrist, or distal forearm.

## Clinical Protocol FIH-3

Doc No: CLINP1837  
Revision: D  
DCO No: 25-009  
Effective Date: 02/06/25

# Clinical Protocol

## FIH-3

Doc No: CLINP1837  
 Revision: D  
 DCO No: 25-009  
 Effective Date: 02/06/25

Publication	Overview	Safety Data																																																																																																																																																																																																																																										
		mitigate risk of mechanical complications including pneumothorax, hemothorax, arterial puncture, hematoma formation, and malposition of central venous catheter.																																																																																																																																																																																																																																										
Shafique, et al "Hemodialysis Internal Jugular Vein Versus Subclavian Vein Catheters: Complications, Patients' Comfort, Tolerance and Cost-Effectiveness" Pak J Med Sci. 2019;35(1):124- 128.	Single-center experience of n = 66 hemodialysis patients with internal jugular vein and subclavian vein catheters	
Table-I: Hemodialysis catheter-related early complications.
 
  
 Variable	Population	OR (95% CI)	
 
 SCV catheter	IJV catheter	
   
 Vein damage: % (f)	6.5 (2)	13.9 (4)	2.15 (0.364 - 12.693)	
 
 Artery rupture	3.2 (1)	9.7 (3)	3.21 (0.316 - 32.741)	
 
 Pulmonary complications	3.2 (1)	3.2 (1)	1.0 (0.060 - 16.737)	
 
 Bacterial infection*	6.5 (2)	6.5 (2)	1.0 (0.132 - 7.587)	
  
 
*exit-site infection; p >0.05 (after chi-squared/Fisher's exact test) against all variables.
 
Table-II: Hemodialysis catheter-related late complications.
 
  
 Variable	Population	OR (95% CI)	
 
 SCV catheter	IJV catheter	
   
 Device dysfunction: % (f)	3.2 (1)	9.7 (3)	3.21 (0.316 - 32.741)	
 
 Thrombus formation*	3.2 (1)	3.2 (1)	1.0 (0.060 - 16.737)	
 
 Central vein stenosis	19.4 (6)	25.8 (8)	1.45 (0.436 - 4.814)	
 
 Bacterial infection	16.1 (5)	32.3 (10)	2.48 (0.733 - 8.369)	
 
 Infection-based replacement	12.9 (4)	25.8 (8)	2.35 (0.645 - 8.814)	
  
 
*managed through catheter removal and systemic anticoagulation.
	Variable	Population		OR (95% CI)	SCV catheter	IJV catheter	Vein damage: % (f)	6.5 (2)	13.9 (4)	2.15 (0.364 - 12.693)	Artery rupture	3.2 (1)	9.7 (3)	3.21 (0.316 - 32.741)	Pulmonary complications	3.2 (1)	3.2 (1)	1.0 (0.060 - 16.737)	Bacterial infection*	6.5 (2)	6.5 (2)	1.0 (0.132 - 7.587)	Variable	Population		OR (95% CI)	SCV catheter	IJV catheter	Device dysfunction: % (f)	3.2 (1)	9.7 (3)	3.21 (0.316 - 32.741)	Thrombus formation*	3.2 (1)	3.2 (1)	1.0 (0.060 - 16.737)	Central vein stenosis	19.4 (6)	25.8 (8)	1.45 (0.436 - 4.814)	Bacterial infection	16.1 (5)	32.3 (10)	2.48 (0.733 - 8.369)	Infection-based replacement	12.9 (4)	25.8 (8)	2.35 (0.645 - 8.814)																																																																																																																																																																																										
Variable	Population			OR (95% CI)																																																																																																																																																																																																																																								
	SCV catheter	IJV catheter																																																																																																																																																																																																																																										
Vein damage: % (f)	6.5 (2)	13.9 (4)	2.15 (0.364 - 12.693)																																																																																																																																																																																																																																									
Artery rupture	3.2 (1)	9.7 (3)	3.21 (0.316 - 32.741)																																																																																																																																																																																																																																									
Pulmonary complications	3.2 (1)	3.2 (1)	1.0 (0.060 - 16.737)																																																																																																																																																																																																																																									
Bacterial infection*	6.5 (2)	6.5 (2)	1.0 (0.132 - 7.587)																																																																																																																																																																																																																																									
Variable	Population		OR (95% CI)																																																																																																																																																																																																																																									
	SCV catheter	IJV catheter																																																																																																																																																																																																																																										
Device dysfunction: % (f)	3.2 (1)	9.7 (3)	3.21 (0.316 - 32.741)																																																																																																																																																																																																																																									
Thrombus formation*	3.2 (1)	3.2 (1)	1.0 (0.060 - 16.737)																																																																																																																																																																																																																																									
Central vein stenosis	19.4 (6)	25.8 (8)	1.45 (0.436 - 4.814)																																																																																																																																																																																																																																									
Bacterial infection	16.1 (5)	32.3 (10)	2.48 (0.733 - 8.369)																																																																																																																																																																																																																																									
Infection-based replacement	12.9 (4)	25.8 (8)	2.35 (0.645 - 8.814)																																																																																																																																																																																																																																									
Cavallazzi, et al. "Central Venous Access Sites for the Prevention of Venous Thrombosis, Stenosis and Infection (Review)" Cochrane Database of Systematic Reviews 2012, Issue 3. Art. No.: CD004084.DOI: 10.1002 /14651858.CD004084.pub3.	Systematic literature review comparing internal jugular vein and subclavian vein: catheter-related infection rates; thrombotic complications; immediate mechanical complications; and late mechanical complications.	
Analysis 1.1. Comparison 1 Internal jugular versus subclavian CVA routes: long-term catheterization, Outcome 1 Catheter related infectious complications.
 
  
 Study or subgroup	Internal jugular n/N	Subclavian n/N	Risk Ratio M-H, Random, 95% CI	Weight	Risk Ratio M-H, Random, 95% CI	
   
 1.1.1 Exit site infection						
 
 Wang 2006	7/100	1/100				
 
 Subtotal (95% CI)	100	100				
 
 Total events: 7 (Internal jugular), 1 (Subclavian)						
 
 Heterogeneity: Not applicable						
 
 Test for overall effect: Z=1.84(P=0.07)						
  
 
Analysis 1.2. Comparison 2 Internal jugular and/or pocket infections
 
  
 Study or subgroup	Internal jugular n/N	Subclavian n/N	Risk Ratio M-H, Random, 95% CI	Weight	Risk Ratio M-H, Random, 95% CI	
   
 1.1.2 Port-related bacteraemia and/or pocket infections						
 
 Biffi 2009	1/117	3/123				
 
 Subtotal (95% CI)	117	123				
 
 Total events: 1 (Internal jugular), 3 (Subclavian)						
 
 Heterogeneity: Not applicable						
 
 Test for overall effect: Z=0.91(P=0.36)						
  
 
Analysis 1.3. Comparison 2 Internal jugular versus subclavian CVA routes: long-term catheterization, Outcome 3 Immediate mechanical complications.
 
  
 Study or subgroup	Internal jugular n/N	Subclavian n/N	Risk Ratio M-H, Random, 95% CI	Weight	Risk Ratio M-H, Random, 95% CI	
   
 1.3.1 Total mechanical complications						
 
 Biffi 2009	0/132	0/136				
 
 Wang 2006	3/100	3/100				
 
 Subtotal (95% CI)	232	236				
 
 Total events: 3 (Internal jugular), 3 (Subclavian)						
 
 Heterogeneity: Not applicable						
 
 Test for overall effect: Not applicable						
  
 
Analysis 1.3. Comparison 2 Internal jugular versus subclavian CVA routes: long-term catheterization, Outcome 3 Immediate mechanical complications.
 
  
 Study or subgroup	Internal jugular n/N	Subclavian n/N	Risk Ratio M-H, Random, 95% CI	Weight	Risk Ratio M-H, Random, 95% CI	
   
 1.3.2 Major mechanical complications						
 
 Biffi 2009	0/132	0/136				
 
 Wang 2006	0/100	1/100				
 
 Subtotal (95% CI)	232	236				
 
 Total events: 0 (Internal jugular), 1 (Subclavian)						
 
 Heterogeneity: Not applicable						
 
 Test for overall effect: Z=0.68(P=0.5)						
 
 Test for subgroup differences: Chi=0.37, df=1 (P=0.54), I=0%						
  
 
Analysis 1.4. Comparison 1 Internal jugular versus subclavian CVA routes: long-term catheterization, Outcome 4 Late mechanical complications.
 
  
 Study or subgroup	Internal jugular n/N	Subclavian n/N	Risk Ratio M-H, Random, 95% CI	Weight	Risk Ratio M-H, Random, 95% CI	
   
 1.4.1 Late mechanical complications						
 
 Biffi 2009	0/132	0/136				
 
 Wang 2006	5/100	3/100				
 
 Subtotal (95% CI)	232	236				
 
 Total events: 5 (Internal jugular), 3 (Subclavian)						
 
 Heterogeneity: Not applicable						
 
 Test for overall effect: Z=0.24(P=0.81)						
  
	Study or subgroup	Internal jugular n/N	Subclavian n/N	Risk Ratio M-H, Random, 95% CI	Weight	Risk Ratio M-H, Random, 95% CI	1.1.1 Exit site infection						Wang 2006	7/100	1/100				Subtotal (95% CI)	100	100				Total events: 7 (Internal jugular), 1 (Subclavian)						Heterogeneity: Not applicable						Test for overall effect: Z=1.84(P=0.07)						Study or subgroup	Internal jugular n/N	Subclavian n/N	Risk Ratio M-H, Random, 95% CI	Weight	Risk Ratio M-H, Random, 95% CI	1.1.2 Port-related bacteraemia and/or pocket infections						Biffi 2009	1/117	3/123				Subtotal (95% CI)	117	123				Total events: 1 (Internal jugular), 3 (Subclavian)						Heterogeneity: Not applicable						Test for overall effect: Z=0.91(P=0.36)						Study or subgroup	Internal jugular n/N	Subclavian n/N	Risk Ratio M-H, Random, 95% CI	Weight	Risk Ratio M-H, Random, 95% CI	1.3.1 Total mechanical complications						Biffi 2009	0/132	0/136				Wang 2006	3/100	3/100				Subtotal (95% CI)	232	236				Total events: 3 (Internal jugular), 3 (Subclavian)						Heterogeneity: Not applicable						Test for overall effect: Not applicable						Study or subgroup	Internal jugular n/N	Subclavian n/N	Risk Ratio M-H, Random, 95% CI	Weight	Risk Ratio M-H, Random, 95% CI	1.3.2 Major mechanical complications						Biffi 2009	0/132	0/136				Wang 2006	0/100	1/100				Subtotal (95% CI)	232	236				Total events: 0 (Internal jugular), 1 (Subclavian)						Heterogeneity: Not applicable						Test for overall effect: Z=0.68(P=0.5)						Test for subgroup differences: Chi  =0.37, df=1 (P=0.54), I  =0%						Study or subgroup	Internal jugular n/N	Subclavian n/N	Risk Ratio M-H, Random, 95% CI	Weight	Risk Ratio M-H, Random, 95% CI	1.4.1 Late mechanical complications						Biffi 2009	0/132	0/136				Wang 2006	5/100	3/100				Subtotal (95% CI)	232	236				Total events: 5 (Internal jugular), 3 (Subclavian)						Heterogeneity: Not applicable						Test for overall effect: Z=0.24(P=0.81)					
Study or subgroup	Internal jugular n/N	Subclavian n/N	Risk Ratio M-H, Random, 95% CI	Weight	Risk Ratio M-H, Random, 95% CI																																																																																																																																																																																																																																							
